9.2. Participants, Recruitment and Criteria of Selection

9.2.1. Participants

The participants of this research will be children with CP GMFCS level III-IV, aged 4 to 12 years and receiving physiotherapy services.

For the sample size ([Annex I](#)), help will be requested from a statistician, and it will depend on factors such as the expected effect size based on previous studies or clinical knowledge, the level of statistical power desired and the level of significance. For example, knowing that similar studies have a sample size of 30, which is always their limitation, a medium effect size is expected, a power of 80% is desired and 0.5 is considered as the level of significance, a sample size of around 64 participants (32 in each group) might be appropriate. However, this sample size might need to be adjusted based on the recruitment rate, dropout rate, and effect size observed during the study.

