9.6. Data Analysis

All data collected from the assessments, questionnaires and the logbook will be analysed using appropriate statistical methods with the help of an expert statistician to achieve the aims of this research protocol. The statistical analyses will be conducted using a statistical software package such as JASP and the statistical significance will be set at p-value <0.05 and CI (Confidence Interval) 95%. When p-value $< 0,05$, the null hypothesis (H_0) will be rejected meaning that the results are statistically significant. The H_0 is: There is no significant difference between the effectiveness of play therapy-based physiotherapy programs and conventional physiotherapy programs in improving treatment adherence and gross motor function in children with cerebral palsy GMFCS level III-IV.

After collecting all data, it will be placed into a spreadsheet for basic data cleaning and categorization ([Annex V](#)). Descriptive statistics (e.g., mean, median, standard deviation, range...) will be calculated to summarize quantitative variables such as age, attendance rate, treatment adherence logbook, GAS score, GMFM-88 score and CP QOL-Child score, while frequency distributions and percentages will be used to summarize categorical variables such as gender, GMFCS level (III or IV), socio-economic status, ethnicity, and type of intervention. All that describes the participants' demographic and baseline characteristics, as well as analyses the distribution of the variables of interest.

Statistical analysis will be done to test the hypothesis using appropriate methodologies based on the data distribution and characteristics. For quantitative variables, t-tests or ANOVA may be used to compare means between the two groups (play therapy-based physiotherapy versus conventional physiotherapy). However, for categorical variables, chi-square or Fisher's exact test might be used, but in this study, it may not be necessary as the hypothesis doesn't include categorical variables.

Moreover, linear regression analysis may be used to investigate the association between treatment adherence and gross motor function while to identify predictors of treatment adherence, gross motor function and quality of life, including age, gender, GMFCS level, social-economic status, ethnicity, and treatment group so potential confounding variables will be controlled for in the

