The study will strictly follow ethical guidelines to protect the rights and welfare of the participants. Before the beginning of the study, all subjects will have to provide informed consent signed. Before the informed consent (IC), a full verbal explanation will be done where all questions will be answered. The informed consent ([Annex VI](#)) will include a full explanation of the study's aims, methods, possible risks, and benefits, as well as the confidentiality safeguards that will be put in place. Participants will have the option to withdraw from the research at any moment with no consequences.

The privacy, anonymity and confidentiality of the participants will be rigorously protected. All personal and medical information will be kept strictly secret and only authorized professionals involved in the study will have access to it. Instead of using their names, participants' identities will be secured by providing them unique identification numbers.

Data collected during the study will be analysed and reported in a way that protects the privacy and confidentiality of the participants. Participants and parents or guardians will be able to know the results of the study at any moment.

All potential risks or damage to participants will be minimized. The research therapies are considered to be safe and are widely used in clinical practice. Throughout the study, adverse events will be observed and recorded, and appropriate actions will be taken to manage and report them as needed.

The research will be carried out in accordance with the relevant laws and regulations, as well as ethical guidelines such as the Declaration of Helsinki and Good Clinical Practice. Prior to the start of the study, a corresponding Institutional Review Board (IRB) or an independent ethical committee will examine and approve the study protocol.

11. Workplan

I will use a work plan in the form of a table chronogram (Table 1) to successfully plan and execute this research project. Each task, its timing, and the person responsible will be specified in the table which is separated into the phases of the project. This will make it easier to track progress and guarantee that all components of the project are completed on time. This will be used to increase efficiency and guarantee that the study is done within the timeframe specified while keeping a high level of quality.

The work plan is divided into 4 phases:

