- Phase I → During this phase, the project proposal and the research design will be developed. The resources needed for the study will be identified and potential foundation will be looked for. It will end with the approval from the ethical committee and the recruitment of the research team.
- Phase II → During this phase, the recruitment and initial screening will be done. The intervention and the assessment will be carried out and will end with the follow-up assessment.
- Phase III → The analysis and interpretation of the results will be done and the final report will be written.
- Phase IV → Is the last part of the project and it's not time-defined because depending on when the project is finished it will be longer or shorter, but the aim of this phase is to ensure that the study findings are disseminated.

This work plan is just a prediction of how it should be conducted but is subjected to changes based on factors such as recruitment rate, dropout rate and effect size observed during the study. Moreover, there are several people that will be in charge of different tasks, that's why in the Table 2 you can find the description of the role and responsibilities of each member.

Role	Responsibilities
Principal Researcher (PR)	
• Develop the research question and design the research protocol• Obtain funding if necessary

	
 • Supervise research execution and ensure that ethical requirements are followed • Supervise research team and delegate tasks • Analyse study data and interpret results • Write and publish the final report and do the dissemination
Research Assistants (RAs)	
 • Assist the principal researcher with administrative tasks and help tracking study progress • Recruit participants and obtain informed consent • Collect and manage data • Assist with interpretation of results and dissemination of findings
Statistician (ST)	
 • Assists with sample size calculation and randomization • Helps in developing the data analysis plan • Conducts statistical analyses • Assists in the interpretation of statistical findings
Outcome Assessors (OAs)	
 • They will be physiotherapists trained for ensuring that the measures are administrated consistently across all participants • They will not know the participant allocation • Administer and score assessments for gross motor function measure.

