15.1. Annex I: Calculation of the Sample Size

For calculating the sample size the following formula have been used (F, G):

$$n = \frac{2SD^2(Z_{\alpha/2} + Z_{\beta})^2}{d^2}$$

Where:

- **n** = sample size
- **Z $\alpha/2$** = the Z-score for the desired level of significance so for 95% confidence level $\alpha=0.05$, $Z_{\alpha/2} = 0.05/2 = 0.025$. This from Z table is **1.96**.
- **Z β** = the Z-score for the desired statistical power so for 80% power where β is 0.20, $Z_{\beta} = 0.8416$ from the Z table.
- **SD** = the estimated standard deviation of the outcome variable based on other studies is **2.43** (18).
- **d** = the effect size (difference in means divided by the pooled standard deviation) taking into account the previous study (18) it will be **1.2**.

Having into account all this, the sample size should be:

$$n = \frac{2SD^2(Z_{\alpha/2} + Z_{\beta})^2}{d^2}; n = \frac{2 \times 2.43^2 (1.96 + 0.8416)^2}{1.2^2}; n = 64.37 \approx 64 \text{ participants}$$

Sample size = 64 participants.

Remember that this sample size may need to be adjusted by a statistician based on factors such as recruitment rate and expected dropout rate.

F: Charan J, Biswas T. How to calculate sample size for different study designs in medical research? Indian J Psychol Med. 2013 Apr;35(2):121-6.
G. Kadam P, Bhalerao S. Sample size calculation. Int J Ayurveda Res. 2010 Jan;1(1):55-7.

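### Section 9.2.1 lets the sample size change on the observed effect size, with no rule and an unadjusted test at 0.05, which can inflate type I error

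*Protocol*

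**What the plan says.** Section 9.2.1 plans about 64 children, 32 per group, and then adds that "this sample size might need to be adjusted based on the recruitment rate, dropout rate, and effect size observed during the study". The same paragraph has already named the effect size expected from earlier studies as a planning input, so the effect observed in the trial is a further quantity. Section 11 says of the work plan that it "is subjected to changes based on factors such as recruitment rate, dropout rate and effect size observed during the study"; that sentence concerns the schedule.

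Section 9.6 sets the test: "statistical significance will be set at p-value <0.05 and CI (Confidence Interval) 95" percent. No interim analysis, adaptation rule, maximum size or adjusted test is described. Section 9.6 places cleaning and analysis after data collection, the section 11 chronogram puts analysis only in Phase III, and Annex I names recruitment rate and expected dropout as example reasons to adjust the size.

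On access to results, section 10 says: "Participants and parents or guardians will be able to know the results of the study at any moment".

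**The concern.** Recruitment and dropout carry no information about the treatment difference, so adjusting for them leaves the 5% level alone. The observed effect size is different: it can be known only by comparing the groups while the trial runs. If the final size then depends on that comparison, the ordinary test statistic no longer has its nominal null distribution, and the chance of a false positive depends on the rule followed. With no rule written down, nobody can show that 5% is kept.

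The clause could well be used. On the protocol's own inputs, 32 per group gives only about 51% power, so a non-significant result is about as likely as not even if the assumed effect is real. That is the situation in which an extension tempts.

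**Working it through.** **Inputs.** From Annex I: SD 2.43, difference 1.2, z values 1.96 and 0.8416, hence two-sided 0.05 and 80% power. From section 9.2.1: 32 per group and "a power of 80% is desired". Section 9.2.1 also prints "0.5 is considered as the level of significance"; I use 0.05, as in section 9.6 and Annex I, and treat the 0.5 as a separate error.

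**The plan's own figure.** 2 × 2.43² × (1.96 + 0.8416)² / 1.2² = 64.37, as printed. This formula gives the number per group (65 per group, 130 in total), whereas the protocol takes 64 as the total. That is also a separate error, but it sets the power at the planned size:
- With 1.2 and 2.43: 1.2 / (2.43 × √(2/32)) = 1.975; 1.975 − 1.96 = 0.015; power = Φ(0.015) = 50.6%.
- With a medium effect taken as 0.5 (my assumption; 1.2/2.43 = 0.49): 0.5 / √(2/32) − 1.96 = 0.04; power = 51.6%.

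**Type I error under assumed rules.** The protocol states no rule, so every rule here is an assumption. Let n₁ per group be the size at the look (25%, 50% or 75% of 32) and z₁ the interim statistic. The size giving 80% power for the observed effect is n = 2 × 2.8016² / (2z₁²/n₁) = 7.849 n₁/z₁². With n₂ = n − n₁ and z₂ from the new data, the ordinary final statistic is (√n₁ z₁ + √n₂ z₂)/√n, rejected beyond ±1.96. I simulated 2 million null trials per rule with known SD (simulation error about 0.0002).

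| Assumed rule | Type I error |
|---|---|
| Size reset up or down, cap 64 or 128 per group | 0.063 to 0.076 |
| Increase only, cap 64 or 128 | 0.057 to 0.069 |
| Decrease only, never above 32 | 0.051 to 0.067 |
| Test at 32 per group; double if p is 0.05 to 0.20 | 0.067 |
| Same; double if p is 0.05 to 0.50 | 0.079 |
| Same; double whenever not significant | 0.083 |
| Extend only if conditional power is 50% to 80% (promising) | 0.043 to 0.050 |
| Extend only if the required size is within the cap | 0.044 to 0.051 |
| Stop early if p<0.05, otherwise go on to 32 | 0.073 to 0.091 |
| Stop early if p<0.05, otherwise extend | 0.087 to 0.100 |

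The last two rows need early stopping for significance, which the protocol does not mention.

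**Worst case for one unrestricted adaptation.** Per side, the known maximum is α + exp(−z²/2)/4 = 0.025 + exp(−1.96²/2)/4 = 0.0616. Doubling gives 0.123. This is an upper bound, because one choice of n₂ cannot be worst for both tails. Choosing n₂ for each z₁ to maximise the chance that the final |z| exceeds 1.96, and averaging over z₁, gives 0.112.

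**With a valid test.** A fixed-weight combination statistic, (z₁ + z₂)/√2 for a half-way look, gives 0.0498 even though n depends on z₁.

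**The case against.** The strongest reply is that no adaptation is planned. Analysis follows data collection, the chronogram has no interim task, the statistician is budgeted for one month (Table 3), the logbook is handed over only at the end of the 16 weeks, and Annex I names only recruitment and dropout. The clause would then be loose wording. Details of an interim analysis are also commonly left to a statistical analysis plan, which is not at hand.

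Much of this stands. The documents do not support several stronger readings:
- **A planned unblinded interim analysis with early stopping.** A reader might infer one, but no look, timing or stopping rule is described.
- **Certain inflation.** A reader might infer that the clause must raise type I error. Two of the assumed rules stay at about 5% or below, so it can inflate the error but need not.
- **Section 11 as a second authority to change the sample size.** Its sentence is about the work plan.
- **Section 10 as a source of type I error.** Telling families results adds no hypothesis test, and that section does not say that comparative interim results will exist.

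What the reply does not remove is that section 9.2.1 itself names the observed effect as a ground for changing the size, and section 9.6 itself fixes the unadjusted 0.05. A later plan could restrict this, but the protocol as written permits it and conflicts with its own fixed-sample description.

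**Conclusion.** The point holds in limited form. Section 9.2.1 permits an effect-driven change of sample size with no rule, cap or adjusted test, and this is at odds with Annex I and with analysis only after data collection. Depending on the rule used, type I error can rise to about 6% to 8% for a single adaptation, with an upper bound of about 12%, or can stay at about 5% or below if the trial is extended only on a promising result. These figures rest on assumed rules, one look, a normal outcome and known SD; the document itself fixes no amount. The clause matters more because power at 32 per group is only about 51%.

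The section 10 sentence is a bias point only. Families and physiotherapists are unblinded (section 9.1), parents complete the CP QoL-Child (section 9.5), and physiotherapists record the adherence logbook, in which parents' following of recommendations scores one point (Annex IV). Comparative results known mid-trial could influence these outcomes. The GMFM-88 is protected to a degree by blinded assessors.

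**What to change.** In section 9.2.1, delete the observed effect size as a ground for adjustment, and allow changes only for recruitment, dropout and a pooled SD estimated without group labels. Make the same deletion in the work-plan sentence of section 11 for consistency. Re-estimation limited to these quantities essentially keeps 5% (a standard result, not simulated here).

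If the sponsor wants to keep an effect-driven change, pre-specify the timing, the rule, the maximum size, who may see the interim comparison, and a fixed-weight combination test.

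Separately, reword section 10 so that comparative results are released only after the last week-24 visit and database lock; families can still be told their own child's clinical information during the trial.

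The cost is three sentences of wording and the loss of an informal effect-driven extension. No visits or participants are added.

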9.2.2. Recruitment

Participants will be recruited from rehabilitation centres or special education schools which treat children with cerebral palsy GMFCS level III-IV. Potential participants will be screened and chosen based on the inclusion and exclusion criteria. Those who match the inclusion criteria will be invited to participate in the study and an initial screening ([Annex II](#)) will be organized in the same centre where they receive their regular treatment. The research purpose, methodology,

risks and benefits and their rights as study participants, will be explained by a call and, if the parents required, it will be explained face to face. The informed consent will be obtained from the parents or legal guardians before starting the baseline assessment.

To ensure diversity in the sample and be able to identify potential factors in the statistical analysis, efforts will be made to recruit participants from a range of socio-economic backgrounds and ethnicities. All the process will be conducted ethically, respectfully and sensitively to the needs of the group being investigated.

Moreover, the study team should take the appropriate steps to guarantee that all possible participants have equitable access to the study and that the recruitment procedure respects potential participants' and their families' privacy and autonomy.

9.2.3. Field of Research

The intervention will take place at a centre, or a special education school specialised in neuropediatric rehabilitation, where they will have all of the required equipment and space for the intervention sessions, which will be led by qualified physiotherapists with experience treating children with cerebral palsy. Some potential places could be ASPACE or CEE l'Arboç because they are specialised in treating children with these characteristics, have enough space to conduct the interventions (explained in section [12. Necessary Resources](#)) and, as I've done my internship there, it would be easier to arrive at an agreement with them.

9.2.4. Selection Criteria

The inclusive and exclusive criteria are designed to ensure that every participant is representative of the target population and has similar levels of impairments and functional limitations.

The inclusion criteria will be:

- Children diagnosed with cerebral palsy by a paediatric neurologist.
- Aged between 4 and 12 years.

- Classified as level III-IV on the GMFCS (A).
 - Children with level III GMFCS walk with assistive mobility devices as they have limitations walking outdoors and in the community.
 - Children with level IV GMFCS have self-mobility with limitations as children are transported or use power mobility outdoors and in the community.
- Regularly receiving physiotherapy at a rehabilitation centre.
- Able to follow instructions and participate in play-based therapy sessions.
- Parental or guardian inform consent signature.

On the other hand, the exclusion criteria will be:

- Children with other neurological or genetic disorders.
- Children with severe cognitive, communication or comorbidities impairments that would interfere with the assessment of outcomes.
- Any contraindications to physical activity or play-based therapy as assessed by a physician.
- Children who are currently participating in other clinical research which might confuse the study's findings.

9.2.5. Randomization

Participants will be randomly assigned to either the experimental group (play therapy-based physiotherapy program) or the control group (conventional physiotherapy program). However, to guarantee group balance, randomization might be stratified by age, gender and GMFCS level. In addition, allocation concealment will be applied to reduce the risk of bias for the outcome assessors.

To do the stratified randomization, first participants will be categorized by the level of GMFCS (III or IV). Then, they will be divided into two subgroups according to age (4-7 years and 8-12 years) and inside these subgroups they will be divided by gender (male and female). Within each stratum, participants will be randomly allocated to either group using a computer-generated randomization list created by an independent statistician who will not be involved in the study.

A. Palisano R, et al. Development and reliability of a system to classify gross motor function in children with cerebral palsy. *Dev Med Child Neurol.* 1997 Apr;39(4):214-23.

9.3. Intervention

The intervention will consist of two groups: a play therapy-based physiotherapy group (experimental group) and a conventional physiotherapy group (control group).

The play therapy-based physiotherapy group will receive 45 minutes sessions of play therapy-based physiotherapy twice a week for 16 weeks (32 sessions in total). The play therapy-based physiotherapy sessions will be conducted by a trained and licensed physiotherapist and will be planned incorporating playing activities such as ball games, obstacle courses, music, sensory toys, and pretend play combined with standard physiotherapy exercises ([Annex III](#)). All that, based on the child's interests and abilities, with the aim of engaging the child in a pleasant and enjoyable activity that simultaneously enhances gross motor function. Moreover, the physiotherapist will offer feedback and positive reinforcement throughout play therapy sessions to encourage adherence. The therapist will also give advice and assistance to the child as needed to ensure that they can do each exercise safely and efficiently and the family will receive home recommendations based on play to assist their worries and questions.

The conventional physiotherapy group will receive 45 minutes sessions of conventional physiotherapy twice a week for 16 weeks (32 sessions in total). The conventional physiotherapy sessions will also be conducted by a trained and licensed physiotherapist and will include standard physiotherapy exercises following the international clinical practice guideline from 2022 of Jackman M, et al (3). These sessions will be planned for each child's needs and goals, for improving gross motor function and increasing treatment adherence. Moreover, the physiotherapist will offer feedback and positive reinforcement throughout sessions to encourage adherence. The therapist will also give assistance as needed to ensure that they can do each exercise safely and efficiently and the family will receive home recommendations based on their worries and questions.

Both groups will get their respective treatments at the same location, and the study team will rigorously monitor adherence to the intervention program. The study team will also gather information on any adverse events or problems that may occur throughout the intervention.

